9 RISK BENEFIT CONSIDERATIONS

The VasQ is used as an adjunct to standard of care end-to-side fistula. It does not interfere in any way with the anastomosis creation and with acceptable surgical paradigms. In clinical use to date (>50 patients) the VasQ device has not been associated with device related adverse events. The potential benefits of the VasQ are in shaping fistula geometry and supporting the venous wall so as to regulate flow regime, mitigating turbulence, and mitigating intimal hyperplasia. Thus the VasQ is designed to enhance fistula patency.

The VasQ should be implanted by trained professional vascular surgeons. Care should be taken to use the VasQ according to the IFU. The VasQ model should be carefully selected according to instructions for use. There is some risk of VasQ interfering with side branch ligations, however this can be mitigated with training and careful attention to instructions, mainly avoidance of metal clips in ligation of side branches.

Potentially, if incorrectly placed or incorrectly sized, the VasQ can lead to fistula failure which in turn can necessitate additional intervention. This risk can be significantly mitigated by careful model selection, avoidance of metal clips, and careful compliance with the IFU.

Document title: VasQ FDA pivotal Protocol	Document No. CD0121	Revision 12.0 14 March 2021	Page 30 of 42
--	------------------------	-----------------------------------	------------------

Additional potential adverse effects associated with the VasQ may include the complications reported for conventional fistula placement procedure and ESRD patients such as: infection, bleeding, aneurysms, hand ischemia, cardiac failure, need for repeat intervention, or death. In summary, while the potential benefits in mitigating venous disease and regulating flow regime are promising, the risks are mainly due to those associated with any vascular access surgery and the adjunct use of the VasQ to standard fistula creation adds minimal risk which can be mitigated with careful training and compliance with IFU. Other risks associated with ESRD and/or vascular access surgery apply to these patients, but are not expected to be influenced by use of the VasQ.

10 STATISTICAL CONSIDERATIONS

10.1 Design considerations

This is a single-arm study where device effectiveness will be tested by comparing study outcome to a pre-specified performance goal (PG). Safety will be evaluated by descriptive comparisons of specific procedure-related AEs between those observed in this study and those of a large study conducted at the Mayo Clinic. The following two sections explain our approach to assessing safety and effectiveness in this trial.

10.2 Safety

Fistulas, being the gold standard vascular access for decades, have a long history of well-established safety. Data exists for the four non-thrombotic safety events relevant: Steal, Infection, Aneurysm, Seroma. In this section we present safety data available from the literature, which we believe is appropriate for comparison to the safety endpoints observed under this study.

10.2.1 Historical safety data

A search of the literature yielded two papers with data on non-thrombotic complications up to a period of 6 months. Based on these papers, SOC fistula safety can be estimated, whose rates with respect to the steal, infection, aneurysm, and seroma are presented in Table 10-1 below:

Table 10-1: Safety data from literature

Paper	Country	N	Steal (%)	Infection (%)	Aneurysm (%)	Seroma (%)	Overall rate [#]
Schinstock et al. Outcomes of Arteriovenous Fistula Creation after the Fistula First Initiative. Clin J Am Soc Nephrol 6: 1996–2002, 2011	USA	293	5.1	7.5	2.4	1.4	7.5 - 16.4
Dunlop et al. Vascular access: experience with the brachiocephalic fistula. Annals of the Royal College of Surgeons of England (1986) vol. 68	Scotland	77	6.5	2.6	3.9	NR*	6.5 – 13.0

Document title: VasQ FDA pivotal Protocol	Document No. CD0121	Revision 12.0 14 March 2021	Page 31 of 42
--	------------------------	-----------------------------------	------------------

*NR=Not reported

*Assuming no subject experienced more than one AE (which we know is not the case) the rate for experiencing any AE is the sum of the rates. Assuming every subject experienced all of the AEs (which we know is not the case) the rate experiencing any AE is the largest percentage reported

Note that:

- The study done in 1986 reports relatively similar rates to the most recent study. The SOC in this indication has changed little in 40 years so that we can expect older data to be as valid for comparison as newer.
- The Schinstock et al study was done in the Mayo Clinic in the US and included nearly 300 patients. For this reason, we propose it as the main comparison to the data to be collected in our own study.
- Importantly, AE rates are reported separately for the each of the four AEs allowing for a detailed comparison of new treatment to the SOC
- The rates reported in the above table overlap so that the average number of AEs for subjects who had these AEs is more than one. Neither of the papers provides an overall rate of subjects who experienced any of the four AEs.

Several additional papers which report data on one or more of the four complications are provided in Table 10-2 in support of the safety values to which the study observed data can be compared. Overall, it can be observed that values for all 4 events converge around single digit incidence rate for each event.

Table 10-2: Additional safety data from the literature

10.2.2 Methodology for assessing safety

Laminate believes that the most appropriate way for assessing safety in the current study is to compare the rates for each type of AE obtained in the study with those reported in the literature. Such a multidimensional comparison will provide a more complete picture of the VasQ's safety profile than comparing an overall rate combining AEs with different clinical implications. Given the four comparisons, we feel it is most appropriate they be done descriptively. First, because statistical testing would involve 4 separate tests, along with associated issues of Type I Error and power (for success in all 4). Second, as noted, neither study provides overall, non-overlapping rates for these four non-thrombotic AEs, nor can this be obtained from the more detailed data presented in the articles (and shown in the preceding section). For this reason a statistical comparison of overall AEs rate cannot be done.

It is important to add that a descriptive comparison of each of the 4 rates between the current trial and Schinstock et al. is meaningful given that the precision of each of the (relatively small) rates is 2% to 4%; i.e. given the small AE rates involved, the planned N for our study of 116 evaluable patients will provide good precision that, in turn, will provide a meaningful comparison between our rates and those reported by Schinstock et al. In addition, even the upper bound higher rate (16.4%) has a precision of 4%. Precision is here defined as the half width of the two sided, 95% confidence interval computed using the Exact Binomial method.

Consequently, we propose evaluating safety in our trial by presenting the 4 AEs listed along with associated two-sided, 95%, Exact Binomial confidence interval to those presented in Schinstock et al. In conclusion, we feel that the most appropriate safety assessment for the VasQ is by:

- Evaluating each of the four AEs of interest separately
- Presenting safety data with two-sided 95% confidence intervals of high precision; i.e. that are relatively narrow at $\pm 3\%$ to 4%

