Primary patency rate at 6 months post AVF creation as defined for the primary effectiveness endpoint, calculated for the main and supplementary cohorts (upper arm and forearm fistula) combined.

The success rate on this [REDACTED] analysis will be compared to a PG of 55.0%.

Safety

The main safety endpoints are occurrence of the following non-thrombotic safety events at up to 6 months: Steal, Infection, Aneurysm, Seroma. Each of these endpoints will be scored dichotomously for each subject as

0 = did not occur

1 = occurred

Thus, for the main safety analyses this study will have 4 rates assessing safety—one for each of the events enumerated.

COHORT

Sample size

144 subjects will be enrolled in this trial in the US.

1. 129 will be enrolled in the main cohort
2. 15 will be enrolled in the supplementary cohort

Inclusion criteria

1. Main study cohort: Patients referred for creation of a new brachiocephalic fistula who consent to take part in the study and which are not indicated for a more distal fistula per treatment guidelines.
Supplementary study cohort: Patients referred for creation of a new forearm fistula who consent to take part in the study.
2. Male and female participants.
3. Age 18-80 years.
4. Patients willing and able to attend follow up visits over a period of 24 months.

Exclusion criteria

Document title: VasQ FDA pivotal Protocol	Document No. CD0121	Revision 12.0 14 March 2021	Page 7 of 42
--	------------------------	-----------------------------------	-----------------

1. Patients with the planned index procedure being a revision surgery of an existing fistula.
2. Main study cohort: Target artery smaller than 2.5 mm or larger than 6 mm in inner diameter by preoperative ultrasound.
Supplementary study cohort: Target artery smaller than 2 mm or larger than 4.1 mm in inner diameter by preoperative ultrasound.
3. Main study cohort: Target vein smaller than 2.5 mm in inner diameter by preoperative ultrasound.
Supplementary study cohort: Target vein smaller than 2 mm in inner diameter by preoperative ultrasound.
4. Significantly stenotic target vein on the side of surgery ($\geq 50\%$) as diagnosed on preoperative ultrasound. (Scan should include the area between the planned anastomosis site and the Axillary vein.)
5. Unusual anatomy or vessel dimensions (observed on pre-operative ultrasound or intraoperatively) and which preclude adequate fit of the VasQ.
6. Patients with central venous stenosis or obstruction on the side of surgery.

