10.4 Sample size justification

Presentation of sample size in this trial is based on the observed Primary Patency rate meeting a PG of 55% (see Section 10.1). Based on limited historical information on the use of VasQ our conservative estimate of device performance is a Primary Patency rate of 70%. A sample of N = 116 evaluable subjects will provide 90% power to demonstrate VasQ meeting the PG. To account for an approximate 10% dropout rate, 129 subjects will participate in this trial. Power computations are based on Exact Binomial computations with a two-sided Alpha = 0.05, designed to demonstrate that the lower

Document title: VasQ FDA pivotal Protocol	Document No. CD0121	Revision 12.0 14 March 2021	Page 36 of 42
--	------------------------	-----------------------------------	------------------

bound of the 95% Exact Binomial confidence interval about observed Primary Patency is above the 55% PG.

In summary, $N = 129$ subjects will be included in this trial to provide 90% power to demonstrate that the VasQ meets its PG.

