10.5 Analysis sets

10.5.1 Safety

The safety population will consist of all subjects for whom the study device was implanted.

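### Section 10.2.2 overstates the precision of the safety estimates at N = 116: the exact 95% half-width is 7.1% for the 16.4% overall rate (stated 4%) and 5.2% for infection (stated 2% to 4%); steal is marginal.

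*Combined protocol and SAP*

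**What the plan says.** Safety is to be judged descriptively. The rates of steal, infection, aneurysm and seroma are each set beside those of the Mayo Clinic study in Table 10-1 (N = 293). Section 10.2.2 argues that this comparison is meaningful because of its precision, and makes these statements:

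- Definition: "Precision is here defined as the half width of the two sided, 95% confidence interval computed using the Exact Binomial method".
- Sample size behind the claim: "the planned N for our study of 116 evaluable patients will provide good precision".
- The four events: "the precision of each of the (relatively small) rates is 2% to 4" percent.
- The overall rate: "even the upper bound higher rate (16.4%) has a precision of 4" percent.
- Closing bullet: "Presenting safety data with two-sided 95% confidence intervals of high precision", with a range of 3% to 4% attached.

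Two other places bear on which N applies. Section 10.5.1 states: "The safety population will consist of all subjects for whom the study device was implanted". Section 10.4 puts the main cohort at 129, and the synopsis puts total enrolment at 144 with the supplementary cohort included.

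**The concern.** An exact 95% interval around a rate near 16% in 116 patients is much wider than 4 percentage points on each side, so the stated figure looks wrong on its face. Within a single sample size, the half-width also grows as the rate rises from 1.4% to 16.4%. A figure of 4% at 16.4% would therefore imply well under 4% at the individual event rates, which is hard to square with a range reaching 4% for those rates.

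Safety is one of the trial's two objectives. It has no performance goal and no hypothesis test, so the descriptive comparison carries the whole assessment. The precision figures are an explicit part of the plan's reason for calling that comparison meaningful. If they are too favourable, a reader of the plan will expect narrower intervals than the trial can deliver, most of all for infection, which has the highest benchmark rate of the four.

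**Working it through.** **Inputs**

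- Benchmark rates (Table 10-1, Mayo Clinic row): steal 5.1%, infection 7.5%, aneurysm 2.4%, seroma 1.4%. The 16.4% is their sum: 5.1 + 7.5 + 2.4 + 1.4 = 16.4.
- N = 116 evaluable (section 10.2.2). Variants: 129 for the main cohort (section 10.4), 144 for both cohorts (synopsis), 293 for the comparator (Table 10-1).
- Method: two-sided 95% exact binomial (section 10.2.2).

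**Formula** (Clopper-Pearson, with x = N × p)

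- Lower limit = 2.5% quantile of Beta(x, N − x + 1)
- Upper limit = 97.5% quantile of Beta(x + 1, N − x)
- Half-width = (upper − lower) / 2

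**Attempt to reproduce the stated figures at N = 116**

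| Rate | x = 116p | Exact 95% interval | Half-width | Stated |
|---|---|---|---|---|
| Seroma 1.4% | 1.62 | 0.1% to 5.6% | 2.7% | 2% to 4% |
| Aneurysm 2.4% | 2.78 | 0.5% to 7.1% | 3.3% | 2% to 4% |
| Steal 5.1% | 5.92 | 1.9% to 10.8% | 4.5% (4.47%) | 2% to 4% |
| Infection 7.5% | 8.70 | 3.4% to 13.9% | 5.2% | 2% to 4% |
| Overall 16.4% | 19.02 | 10.2% to 24.4% | 7.1% | 4% |

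Worked example for 16.4%: (24.41 − 10.18) / 2 = 7.12 percentage points.

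The result does not depend on using non-integer counts. Infection gives 5.1% at 8/116 and 5.3% at 9/116, steal gives 4.5% at 6/116, and 19/116 gives 7.1%.

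**Does another N or method restore the figures?**

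| Exact 95% half-width | N = 116 | N = 129 | N = 144 | N = 293 |
|---|---|---|---|---|
| Seroma | 2.7% | 2.6% | 2.4% | 1.6% |
| Aneurysm | 3.3% | 3.1% | 2.9% | 1.95% |
| Steal | 4.5% | 4.2% | 3.97% | 2.7% |
| Infection | 5.2% | 4.9% | 4.7% | 3.2% |
| Overall 16.4% | 7.1% | 6.7% | 6.4% | 4.4% |

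At N = 116 the 16.4% rate gives 6.7% by the Wald method, 6.7% by Wilson and 6.1% with a 90% exact interval. Infection gives 4.8% by Wald and 4.9% by Wilson. A 4% exact half-width would need about 353 subjects at a rate of 16.4% and about 192 at 7.5%.

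Only the comparator's N = 293 comes near the stated 4% at 16.4%: 4.4% rounds to 4%. At that N the four events run from 1.6% to 3.2%, which does not match the stated 2% to 4% well. The historical sample size is thus a probable source of the 16.4% figure, but an unproven one.

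**The case against.** Several points can fairly be made for the plan.

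*Most of the four event rates are not misstated.* A reader might infer that the precision claim fails for the safety rates as a whole. It does not. Aneurysm and seroma lie inside 2% to 4% at every N this trial could use. Steal at 4.47% rounds to 4% in whole percentages, is 4.2% at N = 129, and falls inside at N = 144. Only infection clearly fails among the four, by a little over one percentage point at N = 116. This stands and limits the point.

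*The 16.4% sentence may describe the historical study.* It repeats no sample size, and the rate is that study's. But it follows directly on the statement about 116 patients and extends it, so this is the less natural reading. Even if it is accepted, infection remains outside the stated range.

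*The 16.4% is not an analysed endpoint.* It is a ceiling that assumes no patient had two events, which the note to Table 10-1 says is untrue, and section 10.2.2 declines to compare overall rates statistically. The closing bullet likewise concerns the four separate events, so it should not be judged against 16.4%. Both points stand, but the plan still offers the 4% figure as evidence of precision.

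*No safety claim is overturned.* A reader might infer that the trial can exclude much less excess risk than the plan promises. The documents do not support this: they set no margin, no excess to be excluded and no safety success criterion. The plan also gives separate reasons for a descriptive comparison, namely four tests with their error and power problems, and the absence of a non-overlapping overall rate in the literature. Section 10.6.5 requires exact intervals for both studies, so the true widths will be reported whatever the planning text says.

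**Conclusion.** The point holds for two figures. Under the plan's own definition and at its own N of 116, the half-width is 7.1% rather than 4% for the 16.4% rate, and 5.2% rather than at most 4% for infection. Steal (4.5%) is marginal, while aneurysm and seroma are acceptable against 2% to 4%. The upper end of the closing bullet is too low for infection and marginal for steal.

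This rests on the observed rates equalling the benchmark rates, as the plan itself assumes, and on 116 as the denominator. The safety set of all implanted subjects would be larger, 129 or 144 at planned enrolment, but neither restores the infection or 16.4% figure.

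The consequence is an overstated argument for the descriptive comparison. It does not invalidate the comparison, and no test, sample size or reported interval changes. It should be fixed, but it is not critical.

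**What to change.** In section 10.2.2:

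1. Name the N on which the precision is based, and reconcile it with the safety set in section 10.5.1 (116 evaluable, 129 in the main cohort, or 144 in both cohorts).
2. Replace the stated figures with the exact half-widths at that N. At 116 these are about 3% to 5% for the four events and 7% for 16.4%. If the 16.4% sentence was meant to describe the historical study, say so and give 4.4% at N = 293.
3. Change the closing bullet to about 3% to 5% and moderate its description of the intervals as highly precise and narrow.
4. Optionally, show the exact interval expected at each benchmark rate, for example infection 3.4% to 13.9% and steal 1.9% to 10.8% at N = 116.

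The cost is a few lines of text. The only downside is a less favourable stated precision.

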10.3 Effectiveness vs. performance goal

The study is a single-arm trial whose results will be compared to a performance goal (PG). The AVF fistula procedure for vascular access, to which Laminat's results will be compared, is mature as it has been the standard of care in this indication for over 40 years. Moreover, the expected outcomes of this procedure with respect to our primary endpoint are well documented. Consequently, in this trial it is appropriate to specify a PG to which device performance will be compared.

The PG for primary patency rate in this trial is based on rates observed in the relevant literature. The following section describes the review of the literature done.

Document title: VasQ FDA pivotal Protocol	Document No. CD0121	Revision 12.0 14 March 2021	Page 33 of 42
--	------------------------	-----------------------------------	------------------

Two sources of data will be used for [REDACTED] analyses:

- Main study cohort: N 129 U.S. subjects (primary analysis)
- Supplementary study cohort: N = 15 U.S. subjects ([REDACTED] secondary analysis is performed on data combining Main and Supplementary cohorts; $15 + 129 = 144$)

10.3.1 Literature review

Laminate has performed a systematic literature review in order to arrive at a PG for the primary endpoint of Primary Patency.

The literature review included the following steps:

- Identification of search criteria.
- Performing said search in Pubmed.
- Assessing each resulting abstracts.
- Selection of papers for full text appraisal.
- Appraisal of full text documents according to specified criteria.
- Selection of documents to be included in analysis.

Papers published over the last 10 years were searched on March 8, 2016.

The search terms have been selected so as to focus on arteriovenous fistula patients and various possible wordings for patency appraisal:

*((((((("Arteriovenous fistula"[Title]) OR "Arteriovenous fistulae"[Title]) OR "Arteriovenous fistulas"[Title]) OR "AV fistula"[Title]) OR "AV fistulae"[Title]) OR "AV fistulas"[Title]))) AND (((("primary patency") OR "primary failure"[Title/Abstract]))) AND (((("vascular access"[Title/Abstract]) OR "hemodialysis access"[Title/Abstract])))
Filters: 10 years, Humans, English*

This search resulted in 40 papers. 40 abstracts were reviewed in order to select papers for full text analysis. Papers were omitted if they related only to specific populations, focused on alternative specific surgical techniques, specific age groups, salvage procedures, etc. 13 papers were selected for detailed data analysis.

Papers were selected to be included if they had provided 6 months post AVF placement Primary Patency data for a patient population similar to the one defined in this protocol. Five papers including data from 966 patients were included for PG calculations (Table 10-3).

Document title: VasQ FDA pivotal Protocol	Document No. CD0121	Revision 12.0 14 March 2021	Page 34 of 42
--	------------------------	-----------------------------------	------------------

Table 10-3: Papers selected for PG calculations

Paper	Geography	N	Primary Patency rate (%)
Lee et al. Comparison of Survival of Upper Arm Arteriovenous Fistulas and Grafts after Failed Forearm Fistula. J Am Soc Nephrol 18: 1936–1941, 2007	USA	59	50
Chiulli et al. Superior Patency of Upper Arm Arteriovenous Fistulae in High Risk Patients. J Surg Res. 2011 September ; 170(1): 157–164	USA	44	61
Field et al. Primary patency rates of AV fistulae and the effect of patient variables. J Vasc Access 2008; 9: 45-50	United Kingdom	79	57
Schinstock et al. Outcomes of Arteriovenous Fistula Creation after the Fistula First Initiative. Clin J Am Soc Nephrol 6: 1996–2002, 2011	USA	293	50
Huijbregts et al. Hemodialysis Arteriovenous Fistula Patency Revisited: Results of a Prospective, Multicenter Initiative. Clin J Am Soc Nephrol. 2008 May; 3(3): 714–719	Netherlands	491	57

Table 10-4: Cohort data from papers used for PG calculations

Paper	Cohort	Age (Y)	Gender (Male %)	Ethnicity Caucasian %	Diabetes	BMI
Lee et al.	Retrospective review of new elbow fistulas after failed primary fistulas placed during 2000-2004	56	61%	83% black	54%	36% > 30 kg/m
Chiulli et al.	Retrospective review of new elbow fistulas placed during 2004-2009	65.8	97.7%	75%	47.7%	28.2
Field et al.	Retrospective review of new elbow fistulas placed during 2003-2007	61	34.2%	94%	43.1%	Not reported
Schinstock et al.	Retrospective review of new fistulas placed during 2006-2008	65.1	65.2%	88.1%	43.3%	29.8
Huijbregts et al.	Prospectively enrolled during 2004-2005 All hemodialysis patients or patients who had chronic renal failure and required a new permanent vascular access.	64.6	62%	78%	33%	25.1

Document title: VasQ FDA pivotal Protocol	Document No. CD0121	Revision 12.0 14 March 2021	Page 35 of 42
--	------------------------	-----------------------------------	------------------

